AE = adverse event, cfDNA = cell free DNA, DMET = Drug metabolizing enzymes and transporters, eCRF = electronic case report form, ECG = electrocardiogram, ECOG PS = Eastern Cooperative Oncology Group Performance Status, IMP = investigational medicinal product, IRT = Interactive response technology, pCR = pathological complete response, PEPI = Preoperative Endocrine Prognostic Index, PK = pharmacokinetic, pN = pathological node, pT = pathological tumor, QD = once daily, SAE = serious adverse event

- a Procedure:** Assessments to be performed prior to study treatment administration unless otherwise indicated. Informed consent should be signed before any study specific procedures. It can be signed more than 14 days prior to randomization. Screening time indicates in which timeframe exams used to support eligibility have to be done prior to randomization. All the tests or procedures scheduled on D1 should be done at predose time unless otherwise stated.
- b D1** refers to the day the participant receives the initial dose of study treatment which will be a single administration of amcenestant 400 mg or 200 mg QD, or letrozole 2.5 mg QD.
- c Surgery:** The date of surgery should be fixed before randomization takes place. The time between first IMP administration and surgery should be of 14 days and the last dose is planned to be taken the day before surgery. Surgery should be done 1 day after the last IMP administration; however this could exceptionally be extended to a maximum of 48h after last IMP administration. In case of a longer unexpected surgery delay (>48 hours from last IMP administration), all efforts should be done to perform a tumor biopsy no more than 48 hours of last IMP administration.

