5.1 INCLUSION CRITERIA

Participants are eligible to be included in the study only if all of the following criteria apply (in case bilateral breast cancer is diagnosed at the same time, only one location as per Investigator judgment will be selected for all selection and assessment criteria):

Age

- I 01. Participant must be older than 18 years of age inclusive, or country's legal age of majority if the legal adult age is >18 years old at the time of signing the informed consent

Type of participant and disease characteristics

- I 02. Patients with histological or cytological proven diagnosis of invasive breast adenocarcinoma
- I 03. Localized breast cancer eligible for upfront breast conservative surgery or upfront mastectomy: Stage I, Stage II or operable Stage III (excludes T4) (*AJCC Cancer Staging Manual 8th edition 2017*; [15])
- I 04. Participants must be postmenopausal women as defined by one of the following:
- With spontaneous cessation of menses >12 months prior to randomization.
 - Or who have received hormonal replacement therapy but have discontinued this treatment AND have FSH level in the postmenopausal range according to institutional standards (or >34.4 IU/L if institutional range is not available) prior to randomization. (Note: serial FSH measurements are required to confirm postmenopausal status in participants who are not using hormonal replacement therapy and in the absence of amenorrhea >12 months.)
 - Or with status post bilateral surgical oophorectomy.
 - Or post bilateral ovarian ablation through pelvic radiotherapy.
- I 05. A breast tumor size of at least 10 mm in greatest dimension measured by ultrasound
- I 06. Primary tumor must be positive:
- ER ($\geq 1\%$ tumor cell staining by IHC)
 - HER2 non-overexpressing by IHC (0, 1+) or in situ hybridization-negative based on single-probe average HER2 copy number <4.0 signals/cell or dual-probe HER2/centromeric probe for chromosome 17 (CEP17) ratio <2 with an average HER2 copy number <4.0 signals/cell (as per the American Society of Clinical Oncology guidelines).

I 07. Ki67 level of at least 15% at diagnosis from immunohistochemistry of the tumor based on local laboratory results

I 08. ECOG performance status 0-1

Weight

I 09. Not Applicable

Sex

I 10. Female

Informed Consent

I 11. Capable of giving signed informed consent which includes compliance with the requirements and restrictions listed in the informed consent form (ICF) and in this protocol.

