5.2 EXCLUSION CRITERIA

Participants are excluded from the study if any of the following criteria apply:

Medical conditions

E 01. Medical history or ongoing gastrointestinal disorders potentially affecting the absorption of amcenestant or letrozole. Participants unable to swallow normally and to take capsules or tablets. Predictable poor compliance to oral treatment. Participants with known active hepatitis A (positive HA antigen or positive IgM); B (either positive HBs antigen or positive hepatitis B viral DNA test above the lower limit of detection of the assay); C (positive hepatitis C antibody result or quantitative hepatitis C (HCV) ribonucleic acid (RNA) results greater than the lower limits of detection of the assay) infection; or hepatic cirrhosis.

E 02. Participant with any other cancer. Adequately treated basal cell or squamous cell skin cancer or in situ cervical cancer or any other cancer from which the participant has been disease free for >3 years are allowed.

E 03. Evidence of metastatic spread by standard assessment according to local practice.

Prior/concomitant therapy

E 04. Treatment with strong CYP3A inducers within 2 weeks before first study treatment administration or 5 elimination half-lives whichever is longest and cannot be replaced.

E 05. Deleted in Protocol Amendment 02.

- E 06. Treatment with drugs that are sensitive substrates of P-glycoprotein (P-gp) (dabigatran, digoxin, fexofenadine) or of breast cancer resistance protein (BCRP) (rosuvastatin, sulfasalazine) within 2 weeks before first study treatment administration or 5 elimination half-lives whichever is longer.
- E 07. Use of any investigational agent within 4 weeks prior to randomization.
- E 08. Recent use of hormone replacement therapy (last dose ≤ 30 days prior to randomization).
- E 09. Prior anti-cancer treatment is not allowed unless it was completed at least 1 year prior to inclusion into this trial.

Prior/concurrent clinical study experience

- E 10. Previous systemic or local treatment for the new primary breast cancer currently under investigation (including surgery, radiotherapy, cytotoxic and endocrine treatments).

Diagnostic assessments

- E 11. Inadequate hematological function including neutrophils $< 1.5 \times 10^9/L$; platelet count $< 100 \times 10^9/L$, hemoglobin < 8.0 g/dL.

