8 STUDY ASSESSMENTS AND PROCEDURES

Study procedures and their timing are summarized in the SoA ([Section 1.3](#)). Protocol waivers or exemptions are not allowed.

- Adherence to the study design requirements, including those specified in the SoA, is essential and required for study conduct.
- All screening evaluations must be completed and reviewed to confirm that potential participants meet all eligibility criteria. If the participant fails to meet the exclusion criteria related to laboratory assessments at Screening, the laboratory assessments may be performed one more time to assess eligibility.
- Repeat or unscheduled samples may be taken for safety reasons or for technical issues with the samples.
- Additional safety tests (eg, ECG, hematology, coagulation, and clinical chemistry) can be performed whenever clinically indicated.
- The date of surgery should be fixed before randomization takes place. The time between first IMP administration and surgery should be of 14 days. Surgery should be done 1 day after the last IMP administration; however this could exceptionally be extended to a maximum of 48 hours after the last IMP administration. In case of a longer unexpected surgery delay (>48 hours from last IMP administration), all efforts should be done to perform a tumor biopsy no more than 48 hours of last IMP administration.
- The IMP dose will be taken on-site after fasting tests and pre-dose assessment on Day 1 and Day 14.
- For a regional or national emergency declared by a governmental agency, contingency measures are included in Appendix 14: Contingency Measures for a regional or national emergency that is declared by a governmental agency.

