2.3.3 Per-protocol (PP) population

PP population is defined as all participants from the mITT population without relevant deviation(s), which could affect the evaluation of the study drug on the primary endpoint. PP population will be used for sensitivity analysis of the primary endpoint.

Major or critical deviations leading to exclusion from the per-protocol population is defined as follows:

- **Informed consent procedure:**
 - Patient does not sign study informed consent or informed consent is signed after study procedure
- **Inclusion/exclusion criteria:**
 - Patient without histological and cytological proven diagnosis of invasive breast adenocarcinoma
 - The localized breast cancer is not eligible for upfront breast conservative surgery or upfront mastectomy
 - Patient is not postmenopausal as per age and criteria defined in the protocol
 - The breast tumor size is less than 10 mm in short axis measured by ultrasound
 - Patient doesn't have a primary tumor positive in ER or non-overexpressing HER2 per protocol definition
 - Ki67 level is lower than 15% at diagnosis from immunohistochemistry of the tumor based on local laboratory results
 - Ki67 level is lower than 15% at baseline based on central laboratory results
 - Prior anti-cancer treatment was completed <1 year prior to inclusion into this trial
 - Patient is not female
 - Recent use of hormone replacement therapy (last dose \leq 30 days prior to randomization)

- **Concomitant medications/therapy**
 - Protocol prohibited therapy/medication/vaccine administered
- **IMP management:**
 - Patient receives ≤ 10 days or ≥ 16 days of the IMP treatment
- **Randomization procedure:**
 - IMP dispensed without Randomization
 - IMP actually dispensed to the subject is different from the IMP allocated

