2.4.5.1.2 Subgroup analyses

Evaluation of consistency

The consistency of the results from the primary analysis will be evaluated across pre-defined subgroups in patients available in the subgroup of consideration. The subgroups included but not limited are defined in [Table 4](#). Depending upon the study results, additional subgroups may be examined, and subgroups with small sample sizes may be pooled to create a larger meaningful subgroup. For each subgroup, geometric LS-mean of percentage reduction in Ki67 with their associated 95% CIs and geometric LS-mean ratio of proportional change between treatment arms with their associated 95% CIs will be provided for each treatment arm.

Evaluation of interactions

For each pre-defined factor defined in [Table 4](#), log-fold change in Ki67 will be analyzed using linear regression model with terms for the factor, treatment and their interaction, adjusted by log baseline Ki67. The p-value of the test of interaction will be provided.

Other prognostic factors

Since the results from the primary analysis could be impacted by confounding factors, any potential issues will be examined and, if confirmed, exploratory analysis of the primary endpoint will be done accordingly. A multiple linear regression model will be used to identify prognostic factors among the demographic and baseline characteristics factors described in the [Table 4](#) using a stepwise selection procedure with a 15% significance level for removing effects. For significant prognostic factors identified in the multivariate model, the balance between treatment groups will be assessed.

Table 4 - Subgroup analyses

Prognostic factor	Description
Age	<65 years or ≥65 years
Race	Asian or White or Other
Tumor stage	1 or 2 or ≥ 3
Tumor size (greatest dimension)	≥10 mm to < 20mm, ≥ 20mm
Ki67 level at baseline (per central assessment)	<20% or ≥20%
ER H-score at baseline	Low ER+. (H-score 1-100) or moderate ER+ (H-score 101-200) or high ER+ (H-score 201-300).
Progesterone receptor	< 20% vs ≥20%

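### The per-protocol exclusion for tumour size is written on the short axis, while the eligibility criterion and the SAP's own subgroup table use the greatest dimension

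*SAP*

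**What the plan says.** SAP 2.3.3 defines PP as the mITT population without relevant deviations and then lists the major or critical deviations that lead to exclusion. Under the inclusion/exclusion heading of that list stands: "The breast tumor size is less than 10 mm in short axis measured by ultrasound".

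Two other current passages set the size measure differently:

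- Protocol 5.1, I05, requires "A breast tumor size of at least 10 mm in greatest dimension measured by ultrasound".
- SAP 2.4.5.1.2, Table 4, defines a subgroup factor as "Tumor size (greatest dimension"), with categories from 10 mm to below 20 mm, and 20 mm or more.

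Protocol 9.3 leaves the details of the relevant deviations to the SAP, so SAP 2.3.3 is the only operative definition of PP. SAP 2.4.5.1.3 lists two sensitivity analyses for the primary endpoint: one by reader, and one in PP.

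**The concern.** The PP list is meant to remove participants whose protocol deviations could affect the primary endpoint. As worded, the size line tests a different diameter from the one on which participants were admitted. A participant who satisfied I05 can therefore be flagged as a major eligibility deviator without having deviated from anything.

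PP is the only listed sensitivity analysis that alters who is analysed. If eligible pairs are dropped from it, a difference between the mITT and PP results could partly reflect the removal of tumours with a small short axis rather than protocol compliance. The loss would be selective by tumour size and shape. Protocol 9.4.1 also plans the PP repeat for the secondary endpoint of a Ki67 decrease of at least 50%; SAP 2.4.5.2 makes PP optional for secondary endpoints.

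**Working it through.** The plan gives no figure for this rule, so there is nothing to reproduce. The check compares the two criteria.

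**Inputs**

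- Eligibility (Protocol 5.1, I05): greatest dimension L of at least 10 mm.
- PP exclusion (SAP 2.3.3): short axis S below 10 mm.
- Geometry: S cannot exceed L. Write r = S/L, with r at most 1.

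**Step 1: does the SAP rule still catch every I05 failure?** If L < 10, then S ≤ L < 10, so the participant is excluded. Yes.

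**Step 2: does it also exclude eligible participants?** S < 10 means rL < 10, that is L < 10/r. Eligible but excluded tumours are those with 10 ≤ L < 10/r. This range is empty only when r = 1.

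**Step 3: an example.** For a 15 x 8 mm tumour, L = 15 meets I05 and S = 8 triggers exclusion. Here r = 8/15 = 0.533 and 10/r = 18.8 mm, so 15 mm lies inside the excluded range.

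**Step 4: range over assumed axis ratios.** The documents give no distribution of r.

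| Assumed r | Eligible tumours excluded |
|---|---|
| 0.9 | 10 to below 11.1 mm |
| 0.7 | 10 to below 14.3 mm |
| 0.5 | 10 to below 20.0 mm |

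For r of 0.5 or more, all of these fall in the lower size category of SAP Table 4 (10 to below 20 mm). With a more elongated tumour the range would extend past 20 mm.

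**Step 5: cost in precision, for illustration.** Losing k of n pairs per arm widens the standard error by √(n/(n−k)) − 1. Two of the planned 40 gives √(40/38) − 1 = 2.6%. Two of an assumed 20 (enrolment ended early and the achieved number is not stated) gives √(20/18) − 1 = 5.4%. The two lost pairs are an assumption.

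**Step 6: does the rest of the list track the current protocol?** The surgery line does: "The localized breast cancer is not eligible for upfront breast conservative surgery or upfront mastectomy" mirrors I03, "Localized breast cancer eligible for upfront breast conservative surgery or upfront mastectomy". The line on hormone replacement therapy mirrors criterion E08, "Recent use of hormone replacement therapy", with the same limit of 30 days. The size line does not mirror I05.

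**The case against.** The strongest reply is that the short-axis line may be a deliberate, stricter PP rule. The same list contains one: it excludes a central baseline Ki67 below 15%, whereas I07 concerns only the local result. Another line also departs from the protocol, asking for histological *and* cytological proof where I02 accepts either. Agreement of neighbouring lines therefore does not prove intent, and that part of the reply stands. However, the central Ki67 item names its different source and sits beside a separate line that reproduces I07. The size line carries no such label and takes the place of I05. Whatever was intended, the list has no line that tests I05 as it now reads.

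Protocol Appendix 15 records that I05 once used the short axis. That suggests where the wording came from, but the point does not rest on it; the conflict is between current texts.

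A second reply is that the rule may have no effect. The number of eligible participants with a short axis below 10 mm is unknown and may be zero. The documents do not show the data field for screening ultrasound. The response criteria in Protocol Appendix 11 use the product of the longest and perpendicular diameters, which suggests that a second diameter may be recorded, but they also allow one-dimensional measurement. If the short axis is recorded, the rule can exclude eligible participants; if it is not, the rule cannot be applied as written. The correction is the same in either case.

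**Conclusion.** The point holds as a minor error of wording. SAP 2.3.3 contradicts Protocol I05 and SAP Table 4, and no other passage resolves the conflict. Confidence in the contradiction is high. Its practical size is unknown, because it depends on the axis ratios and on whether a short axis is recorded.

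Two stronger readings are not supported:

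- A reader might infer that the main result is affected. It is not: mITT has no size condition, and SAP 2.4 states that no hypothesis test will be performed on the primary endpoint and that confidence intervals are descriptive.
- A reader might infer that the PP list and the sensitivity analyses are also in error because they say nothing about biopsies taken late after the last dose. Protocol 1.3 footnote c says of surgery that "this could exceptionally be extended to a maximum of 48h after last IMP administration", and Section 8 repeats the limit. Yet Section 8.6.1 recommends taking tissue at the planned surgery even when that window is missed, and mITT asks only for paired Ki67 values. Late tissue is thus kept knowingly, and the documents give neither a size nor a direction for any effect of delay. An analysis by biopsy timing would be an optional extra; its absence is not a mistake.

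**What to change.** In SAP 2.3.3, replace the words for short axis with greatest dimension, so that the line excludes tumours below 10 mm in greatest dimension by ultrasound, as I05 and Table 4 imply. Make the same change in any programming specification for the PP flag, and do so before database lock.

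The cost is two words in the SAP. No data collection, treatment, model or primary analysis changes. Every participant who fails I05 is still excluded, so nothing is lost.

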2.3.4 Safety population

Safety population is defined as all participants randomly assigned to study intervention and who take at least 1 dose of study intervention. Participants will be analyzed according to the treatment arm they actually received at Day 1.

Randomized patients from whom it is unclear whether they took the IMP will be included in the safety population, and included in the treatment arms as randomized.

Non-randomized but treated patients will not be part of the safety population; however, their safety data will be presented separately.

This population is the primary population for the analysis of all safety parameters.

2.3.5 Pharmacokinetic population

Pharmacokinetic-evaluable population is defined as all participants from the safety population who receive at least one dose of SAR439859 and with at least 1 available post-treatment plasma concentration with adequate documentation of dosing and sampling dates and times.

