Pathological tumor (pT) stage, the pathological node (pN) stage, pCR and ECOG response assessment, Preoperative Endocrine Prognostic Index (PEPI)					X		Pathological tumor (pT) stage, the pathological node (pN) stage, and pCR results will be collected from the local pathologist's report following examination of tissue (breast and nodes) removed at the time of surgery and reported in eCRF. ECOG response will be assessed by the investigator according to ECOG response criteria. See Section 8.1.1 and Section 8.1.3 for details.
AE/SAE review	←=====→						AEs of new onset as well as worsening of baseline signs and symptoms are to be reported from the signing of the informed consent to 30 (±7) days following the last IMP intake. All SAEs, and non-serious AEs of special interest, and non-serious AEs related to IMP still ongoing at the post treatment safety follow-up visit, will be followed until resolution, stabilization, the event is otherwise explained, or the participant is lost to follow-up. See Section 8.3 for details.
Concomitant medication	←=====→						The period of collection of concomitant medications extends from the signing of the informed consent to 30 (±7) days following the last IMP intake. See Section 6.5 for details.

Procedure ^a	Screening	Treatment Period (14 days)			Surgery ^c	Post treatment safety follow-up period	Notes
	up to 14 days before randomization	D1 ^b	D7 (±2)	D14	D15 (+1)	30 (±7) days after last IMP intake	
Genetic sample (plasma for cfDNA)		X		X			cfDNA sample collected on D1 and D14. See Section 8.7 for details.
Genetic sample (saliva for reference DNA)		X					Saliva will be collected on D1 to extract DNA which will be used as a normal reference for the mutation analysis. See Section 8.7 for details
Genetic sample (blood for DMET genotyping)		X					Blood sample will be collected on Day 1 for amcenestant treatment arms only. See Section 8.7 for details
Amcenestant PK				X	X		PK sampling is planned only for amcenestant treatment arms. D14: Pre-dose (P00), T3h post dose (P01) D15: T24h post dose (P02) after last administration of amcenestant (D14) When PK and triplicate ECG are scheduled at the same time, PK sample will be taken just after ECG recording. Participants will take IMP on-site on days of PK sampling. See Section 8.5 for details.

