Pharmacokinetic data were obtained from two Phase 1 studies: one study in healthy post-menopausal women after a single dose of 100 to 400 mg and one study mentioned above in mBC patients after repeated QD administration from 20 to 600 mg. From a total of 16 patients dosed QD repeatedly with amcnestrant in Study TED14856, a high variability of exposures was observed after the first dose (average CV >60%) and a moderate variability after repeated administrations (average CV ~ 45%). The PK profile generally showed a rapid absorption (median time to achieve maximum concentration (t_{max}) ~ 3h) followed by a biphasic elimination profile. Overall across doses, apparent volume of distribution was large (~ 120 L), and apparent systemic clearance was low (~ 14-15 L/h). Preliminary data from the single ascending dose study in healthy population (100 to 300 mg in fasted state) showed a terminal half-life around 20 h. A moderate accumulation was observed on Day 21/22 after QD administrations up to 200 mg while no accumulation was observed at higher doses. Exposure (C_{max} , AUC_{0-24h}) increases with the dose after single dose, and up to 400 mg after repeated once daily administrations, slightly less at 600 mg. When given with food, no major increase of exposure was observed (no change on C_{max} and ~ 30 % increase on AUC_{0-24h}) with a delay on t_{max} by 1 hour.

At the time of the dose escalation analyzes, a partial response was observed in 1 patient receiving 150 mg daily, stable disease in 8 patients (50%) and progressive disease in 7 patients (43.8%). In accordance to the results obtained from these three parameters, safety, ¹⁸F-FES-PET scans and pharmacokinetics, the recommended dose of amcnestrant was fixed at 400 mg QD. This recommended dose was established in mBC patients, however for patients with early breast cancer, a lower dose of 200 mg QD is thought to be of interest and is being explored with the assumption that adjuvant therapy is usually 5 years and this will allow selection of the most optimal exposure to therapy.

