6.6 DOSE MODIFICATION

If a dose of IMP is vomited or omitted, the participant should not take the dose later or 2 doses at the next planned dose, and this information has to be recorded in the patient diary and eCRF.

Investigational medicinal product dose omission is allowed in case of severe toxicity and the reason should be documented in the eCRF. Doses omitted for toxicity are not to be replaced after the 14-day treatment period or compensated at the next planned IMP intake during the 14-day treatment period.

Conditions for dose modifications are aligned in [Table 3](#). Please refer to letrozole label information on additional specific contraindications and events requiring use precaution, and instruction of dose modification.

Table 3 - Dose modification for amcenestant arms and letrozole arm

NCI-CTCAE grade	Dose modifications
Grade 1 or 2	No dose adjustment required except for Grade 2 alanine transferase defined as an AESI *
Grade \geq 3	Amcenestant and letrozole should be definitely discontinued. No reintroduction is allowed.

NCI-CTCAE = National Cancer Institute Common Terminology Criteria for Adverse Events.

* See [Section 8.3](#)

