9.3 POPULATIONS FOR ANALYSES

For purposes of analysis, the following populations are defined (Table 4):

Table 4 - Populations for analyses

Population	Description
Enrolled	All participants who sign the informed consent form
Intent-to-treat (ITT) population	All participants from the enrolled population and for whom there is a confirmation of successful allocation of a randomization number by IRT. Participants will be analyzed according to the treatment arm assigned at randomization. This population will be used for analysis of baseline parameters.
Modified ITT (mITT) population	All participants from the ITT population who have taken at least one drug, and who have both baseline and post treatment available biopsies with Ki67 values. This is the primary analysis population for all pharmacodynamic and efficacy parameters
Per-protocol (PP) population	All participants from the mITT population without relevant deviation(s), which could affect the evaluation of the study drug on the primary endpoint. Details of relevant deviations would be further specified in the statistical analysis plan. PP population will be used for sensitivity analysis of the primary endpoint.
Safety	All participants randomly assigned to study intervention and who take at least 1 dose of study intervention. Participants will be analyzed according to the treatment arm they actually received. This population is the primary population for the analysis of all safety parameters
Pharmacokinetic-evaluable	All participants from the safety population who receive at least one dose of amcenestant and with at least 1 evaluable post-treatment plasma concentration.

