2.4.7 Analyses of pharmacokinetic and pharmacodynamic variables

2.4.7.1 Analysis of Pharmacokinetic variables

Plasma concentrations will be summarized for each SAR439859 treatment arm by time point using descriptive statistics (such as the number of observations, arithmetic and geometric mean, median, standard deviation (SD), standard error (SE), coefficient of variation (CV)%, minimum, and maximum).

Plasma concentrations will be included in the descriptive statistics if actual sampling occurs in the following predefined time windows: within 2 hours before administration for predose sample on Day 7, Day 14, [2-4h] for samples at 3h post dose on Day 14 and Day 15;

In addition, a listing of individual concentration data by time and day will be provided.

Concentrations reported as below the limit of quantification (BLQ) will be replaced by 0 for descriptive statistics.

In case PK parameters estimates are calculated and used as part of the PK/PD exploratory analysis, they will be summarized by SAR439859 treatment arm using descriptive statistics (such as the number of observations, arithmetic and geometric mean, median, standard deviation (SD), standard error (SE), coefficient of variation (CV)%, minimum, and maximum).

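### SAP 2.4.7.1 admits PK concentrations on sampling time alone, so Day 14 samples that follow a missed or vomited dose enter the 400 mg and 200 mg QD summaries

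*SAP*

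**What the plan says.** **Population.** Protocol 9.3, Table 4, defines the PK set as safety participants who received amcenestrant "with at least 1 evaluable post-treatment plasma concentration". It does not define *evaluable* for this purpose. SAP 2.3.5 words the condition as "with at least 1 available post-treatment plasma concentration with adequate documentation of dosing and sampling dates and times".

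**Samples.** SAP 2.4.7.1 summarises concentrations by amcenestrant arm and time point, with arithmetic and geometric means among the statistics. The rule for admitting a sample is: "Plasma concentrations will be included in the descriptive statistics if actual sampling occurs in the following predefined time windows". The windows are "within 2 hours before administration for predose sample on Day 7, Day 14" and, as an interval in hours, "2-4h] for samples at 3h post dose on Day 14 and Day 15".

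**Schedule.** Protocol 1.3 plans three samples: Day 14 pre-dose, Day 14 at 3 h, and "D15: T24h post dose (P02) after last administration of amcenestant (D14"). Study drug is taken on site on PK sampling days.

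**Missed doses.** Protocol 6.6 foresees them: "If a dose of IMP is vomited or omitted, the participant should not take the dose later". Such events go into the diary and the eCRF. Protocol 6.4 adds that a participant who takes an extra dose skips the next day's dose. Protocol 8.5 asks for the actual times of previous doses to be recorded.

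**The concern.** The summaries are meant to describe concentrations on 400 mg and 200 mg once daily. The pre-dose window is measured back from the next dose, so it cannot reveal that the previous one was missed. If Day 13 was omitted or vomited, a sample taken an hour before the Day 14 dose is in effect a 48 h concentration, yet it passes. A 3 h sample after a vomited Day 14 dose also falls inside its interval. The documentation condition in SAP 2.3.5 does not help, because a well-documented omission satisfies it.

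The result is a downward shift in the arm's trough and 3 h summaries and a wider spread. If omissions differ between the arms, the two columns are no longer like for like.

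**Working it through.** The documents give no figure on this point to reproduce, so the check compares the rules with the schedule and then sizes the effect.

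**1. Which samples pass**

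- *Day 14 pre-dose, Day 13 dose omitted, vomited or skipped:* passes the 2 h window.
- *Day 14 3 h, Day 14 dose vomited:* passes the 2 to 4 h window.
- *Day 15 at 24 h:* it is neither a pre-dose sample nor a 2 to 4 h sample. Read literally, it is left out whatever the dosing.
- *Day 7 pre-dose:* has a window but is not in the current schedule.

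**2. Inputs (Protocol 4.3)**

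- The single-dose study in healthy women "showed a terminal half-life around 20 h".
- Apparent volume is about 120 L and apparent clearance about 14 to 15 L/h. The implied one-compartment half-life is ln 2 × 120/14 = 5.9 h to ln 2 × 120/15 = 5.5 h.
- The affected share f is assumed; the documents give none.

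**3. Effect in one participant**

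Let r be the fraction of drug left after 24 h.

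- 20 h half-life: r = 2^(−24/20) = 0.435.
- CL/V: r = exp(−24 × 14/120) = 0.061 to exp(−24 × 15/120) = 0.050.

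Ratios to the value with every dose taken:

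- Day 14 trough after a wholly lost Day 13 dose, or 3 h value after a wholly lost Day 14 dose: r. That is a fall of 56% (20 h) or 94% to 95% (CL/V).
- 3 h value when Day 13 was lost but Day 14 was kept: 1 − r(1 − r) = 0.754 (20 h) or 0.943 to 0.953 (CL/V), a fall of 25% or about 5% to 6%.
- Day 14 trough when Day 13 was skipped because of an extra Day 12 dose: 1 − (1 − r)² = 0.68 (20 h) or 0.12 to 0.10 (CL/V). This is milder than a plain omission.

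**4. Effect on the arm's Day 14 trough**

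The arithmetic mean changes by f(r − 1) and the geometric mean by r^f − 1.

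| Share affected (assumed) | 20 h: arithmetic | 20 h: geometric | CL/V: arithmetic | CL/V: geometric |
|---|---|---|---|---|
| 1 in 42 | −1.3% | −2.0% | −2.2% to −2.3% | −6.4% to −6.9% |
| 5% | −2.8% | −4.1% | −4.7% to −4.8% | −13.1% to −13.9% |
| 10% | −5.6% | −8.0% | −9.4% to −9.5% | −24.4% to −25.9% |

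**5. How far back a rule must look**

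A single dose missed j days before the Day 14 trough lowers it by (1 − r)r^(j−1). At 20 h this is 56% for j = 1, 0.565 × 0.435 = 25% for j = 2, and 0.565 × 0.435³ = about 5% for j = 4. Under CL/V the j = 2 effect is already only 5% to 6%.

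**The case against.** Four parts of the opposing case stand.

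- *Few samples are exposed.* Dosing is on site on PK days, and under Protocol 7.1.1 participants who stop early have no PK sampling at the later visits. What remains is mainly a lost Day 13 dose and vomiting on Day 14. Phase 1 reported vomiting in 2 of 16 patients, but at any time on treatment rather than on one given day.
- *The model is crude.* With r = 0.435 it predicts accumulation of 1/(1 − 0.435) = 1.77, whereas Protocol 4.3 reports a biphasic decline and no accumulation above 200 mg. The 20 h figures therefore fit the 400 mg arm poorly, and the two half-lives only bracket the answer.
- *Some of this is visible already.* Medians and individual concentrations are reported, and SAP 2.4.4 tabulates omissions by arm.
- *A long look-back would discard too much,* as step 5 shows.

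A reader might also infer more than the documents support:

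- *That the SAP loosened the protocol by writing available for evaluable.* The protocol leaves *evaluable* undefined and the SAP adds a documentation requirement, so no loosening can be shown. Restoring the word alone would settle nothing. SAP 2.3.5 also selects participants, not samples; the gap is in 2.4.7.1.
- *That Day 15 samples are averaged in after missed doses.* They fit no window and would be dropped.
- *That the table is presented as steady-state exposure, or selects the dose.* Neither document uses that label for it, and 2.4.7.1 plans no comparison between arms. The remark in Protocol 4.3 on optimal exposure explains why 200 mg is studied.

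**Conclusion.** The point holds in a narrow form. As written, 2.4.7.1 averages in Day 14 concentrations that do not reflect once-daily dosing, and nothing else in the SAP removes or flags them. For the participant concerned the trough error is large, about 56% to 95% if the dose was wholly lost, and less if it was partly retained. For an arm of 42 with one such participant, the geometric mean falls by about 2% to 7%. Enrolment stopped early (SAP 2.4), so one participant will weigh more than 1 in 42.

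These sizes rest on log-linear one-compartment decline and on an assumed frequency. The window mismatch for Day 15 and Day 7 needs no assumption. PK is a tertiary/exploratory objective and the primary Ki67 analysis does not depend on it, so this is a minor, optional improvement.

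**What to change.** Amend SAP 2.4.7.1 in two respects.

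1. **Dosing rule.** Add: *A concentration is excluded from the descriptive statistics, and flagged in the individual listing, if the dose immediately preceding the sample was omitted, vomited or taken in excess. For the Day 14 3 h sample this applies to the Day 14 and the Day 13 dose.* State that these samples stay in the PK/PD and concentration-ECG analyses (SAP 2.4.9), where the concentration actually reached is the right predictor.
2. **Windows.** Keep the Day 14 pre-dose and 3 h windows, add one for the Day 15 sample around 24 h after the Day 14 dose, and remove Day 7. The PK team should set the Day 15 width, bearing in mind that the Day 15 visit carries a +1 day allowance.

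The rule is deliberately short. It leaves a missed Day 12 dose in the Day 14 trough (5% to 25% by step 5), which the sponsor may accept or extend by one day. The cost is SAP wording, a little programming on dosing data already collected, and a few fewer concentrations in an exploratory table.
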